#### **4.4.1.1 Anti-malarials (E.g., Hydroxychloroquine, Chloroquine)**

Patients taking anti-malarial medications at study entry should be on a stable dose for at least 8 weeks prior to screening and should maintain a constant dosage throughout the study. Patients not previously on anti-malarial medications may be enrolled in the study but should not initiate anti-malarial medications during the course of the blinded study. Replacement of one anti-malarial with another may be allowed in cases where there is limited supply of the original medication, or if there are issues with toxicity or intolerance; however, the change must be discussed with the Medical Monitor. Refer to [Appendix 18](#) for anti-malarial list.

#### **4.4.1.2 Mycophenolate Mofetil/Mycophenolic Acid**

All patients who are taking mycophenolate mofetil (or mycophenolic acid) should be on a stable dose for 8 weeks prior to screening. When mycophenolic acid is used instead of mycophenolate mofetil, a 360-mg dose of mycophenolic acid is considered to be equivalent to a 500-mg dose of mycophenolate mofetil. Mycophenolate mofetil may have an interaction with oral contraceptives that may decrease their effectiveness; however, patients enrolling in this study and using hormonal contraceptives as a method of contraception are required to also use a barrier, such as a male condom.

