- For women of childbearing potential: agreement to remain abstinent (refrain from heterosexual intercourse) or use contraceptive methods that result in a failure rate of < 1% per year during the study treatment period and for a minimum of 60 days after the last dose of study drug or longer as required by local requirements for other standard of care medications. Women using estrogen-containing hormonal contraceptives as a method of contraception must also use a barrier.
  - A woman is considered to be of childbearing potential if she is postmenarcheal, has not reached a postmenopausal state (> 12 continuous months of amenorrhea with no identified cause other than menopause), and has not undergone surgical sterilization (removal of ovaries and/or uterus).
  - Examples of contraceptive methods with a failure rate of < 1% per year include bilateral tubal ligation, male sterilization, hormone-releasing intrauterine devices, and copper intrauterine devices. Established proper use of hormonal contraceptives that inhibit ovulation also have a failure rate of < 1% per year; however, women using estrogen-containing hormonal contraceptives as a method of contraception must also use a barrier, such as a male condom, in conjunction with the hormonal contraceptives.
  - The reliability of sexual abstinence should be evaluated in relation to the duration of the clinical trial and the preferred and usual lifestyle of the patient. Periodic abstinence (e.g., calendar, ovulation, symptothermal, or post-ovulation methods) and withdrawal are not acceptable methods of contraception.
- For men: agreement to remain abstinent (refrain from heterosexual intercourse) or use contraceptive measures, and agreement to refrain from donating sperm as defined below:
  - Men with female partners of childbearing potential must remain abstinent or use a condom plus an additional contraceptive method that together result in a failure rate of < 1% per year during the treatment period and for at least 120 days (16 weeks) after the last dose of study treatment. Men must refrain from donating sperm during this same period.
  - Men with pregnant female partners must remain abstinent or use a condom during the treatment period and for at least 28 days after the last dose of study treatment to avoid exposing the embryo.

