- For women of childbearing potential: agreement to remain abstinent (refrain from heterosexual intercourse) or use contraceptive methods listed in [Appendix 8](#) that result in a failure rate of  $< 1\%$  per year during the study treatment period and for a minimum of 60 days after the last dose of study drug or longer as required by local requirements for other standard of care medications. Women using estrogen-containing hormonal contraceptives as a method of contraception must also use a barrier.
  - A woman is considered to be of childbearing potential if she is postmenarcheal, has not reached a postmenopausal state ( $> 12$  continuous months of amenorrhea with no identified cause other than menopause), and has not undergone surgical sterilization (removal of ovaries and/or uterus).
  - Examples of contraceptive methods with a failure rate of  $< 1\%$  per year include bilateral tubal ligation, male sterilization, hormone-releasing intrauterine

devices, and copper intrauterine devices. Established proper use of hormonal contraceptives that inhibit ovulation also have a failure rate of < 1% per year; however, women using estrogen-containing hormonal contraceptives as a method of contraception must also use a barrier, such as a male condom, in conjunction with the hormonal contraceptives.

- The reliability of sexual abstinence should be evaluated in relation to the duration of the clinical trial and the preferred and usual lifestyle of the patient. Periodic abstinence (e.g., calendar, ovulation, symptothermal, or post-ovulation methods) and withdrawal are not acceptable methods of contraception.
- For men: agreement to remain abstinent (refrain from heterosexual intercourse) or use contraceptive measures, and agreement to refrain from donating sperm as defined below. Please also see [Appendix 8](#) for details:
  - Men with female partners of childbearing potential must remain abstinent or use a condom plus an additional contraceptive method that together result in a failure rate of < 1% per year during the treatment period and for at least 120 days (16 weeks) after the last dose of study treatment. Men must refrain from donating sperm during this same period.
  - Men with pregnant female partners must remain abstinent or use a condom during the treatment period and for at least 28 days after the last dose of study treatment to avoid exposing the embryo.

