#### **4.4.2.2 CYP3A and BCRP-Mediated Drug Interactions**

*Preliminary data from a clinical drug-drug interaction study (Study GP39616) suggest that GDC-0853 may be classified as a mild inhibitor of CYP3A at clinically relevant doses. It is possible that GDC-0853 inhibition of CYP3A may alter the metabolism of CYP3A substrates and result in increased plasma concentrations of CYP3A substrates.*

Therefore, medications in the following categories (listed in detail in [Appendix 19](#)) should be used with caution in consultation with the Medical Monitor (or delegate) as necessary unless otherwise specified in Section 4.4.2:

- Sensitive CYP3A substrates
- CYP3A substrates with a narrow therapeutic index

*The use of hormone-replacement therapy or hormonal contraceptives containing the CYP3A substrate ethinylestradiol (with the concomitant use of a barrier method) is permitted; however, patients should be counseled regarding the potential risks and benefit of these medications per the local prescribing information. Any increase in ethinylestradiol plasma concentrations is anticipated to be modest at most due to the relatively minor contribution of CYP-mediated oxidation in the clearance of orally administered ethinylestradiol (Zhang et al. 2007); however, increased ethinylestradiol plasma concentrations may lead to an increase in common side effects (e.g. nausea, breast tenderness, and headaches) and a theoretical increase in rare dose-related events (e.g. thromboembolism; Inman et al. 1970).*

*Preliminary data from Study GP39616 also suggest that GDC-0853 may be classified as a moderately sensitive substrate of CYP3A at clinically relevant doses. There is a moderate potential for a drug-drug interaction with any medication that strongly inhibits or induces this enzyme. Therefore, medications in the following categories (listed in detail in [Appendix 19](#)) should be avoided for 7 days or 5 half-lives, whichever is longer, prior to the first dose of study drug until the last dose of study drug, unless otherwise advised by the Medical Monitor (or delegate). If use of one of these medications is necessary, the risks and benefits should be discussed with the Medical Monitor prior to concomitant administration with study drug.*

- Strong CYP3A inhibitors
- Moderate or strong CYP3A inducers

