## **Appendix 8**

### **Childbearing Potential, Pregnancy Testing, and Contraception**

#### **For Women**

All women of childbearing potential (including those who have had a tubal ligation) will have a serum pregnancy test at screening and a urine pregnancy test on study day 1 prior to administration of study drug and at subsequent clinic visits. If a urine pregnancy test result is positive, study drug will not be administered until pregnancy is ruled out. The result must be confirmed by a serum pregnancy test (conducted by the local laboratory).

Refer to Section 5.4.3 of the protocol for management of a patient with a confirmed pregnancy.

All female patients are considered to be of childbearing potential unless they meet one of the following criteria:

- The patient has been postmenopausal (non–therapy-induced amenorrhea) for at least 12 continuous months with no other identified cause
- The patient had a surgical bilateral oophorectomy (with or without hysterectomy) more than 6 weeks prior to enrollment
- The patient had a hysterectomy

Female patients of reproductive or childbearing potential who are unwilling to use a method of contraception that results in a failure rate of < 1 % per year or remain abstinent (refrain from heterosexual intercourse) during the treatment period and for at least 60 days after the last dose of study drug, or longer as required by local requirements for other standard of care medications, will be excluded from study participation.

Abstinence is acceptable only if it is in line with the preferred and usual lifestyle of the patient. Periodic abstinence (e.g., calendar, ovulation, symptothermal, or post-ovulation methods) and withdrawal are not acceptable methods of contraception.

Examples of contraceptive methods with a failure rate of < 1% per year include the following:

- Sterilization, bilateral surgical tubal ligation
- Intrauterine device
- Combined oral contraceptive pill\*
- Contraceptive transdermal patch (estrogen and progestin containing)\*
- Hormonal vaginal device
- Progestogen-only hormonal contraception associated with inhibition of ovulation
- Implants for contraception

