## **Appendix 8 Childbearing Potential, Pregnancy Testing, and Contraception (cont.)**

- Injections for contraception (with prolonged release)
- Sole sexual partner consisting of surgically sterilized male partner with appropriate postsurgical verification of the absence of spermatozoa in the ejaculate. Patients may provide verbal confirmation that the partner completed appropriate follow-up after vasectomy. Sites are not required to obtain partner medical records.
- Same sex partner
- \* **Women using estrogen containing hormonal contraceptives as a method of contraception must also use a barrier such as a male condom in conjunction with the hormonal contraceptives.**

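### Section 4.4.1.2 counts on a barrier with every hormonal contraceptive to offset a possible mycophenolate interaction, but the contraception rules in the synopsis, Section 4.1.1 and Appendix 8 require one only with estrogen-containing methods

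*Combined protocol and SAP*

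**What the plan says.** Section 4.4.1.2 permits mycophenolate as background therapy and states a risk: "Mycophenolate mofetil may have an interaction with oral contraceptives that may decrease their effectiveness". The same sentence then offsets the risk by saying that patients in the study "using hormonal contraceptives as a method of contraception are required to also use a barrier, such as a male condom". It does not limit this to estrogen-containing products.

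The texts that set the contraception rules are narrower.

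- **Synopsis and Section 4.1.1**, both in the same words: "Women using estrogen-containing hormonal contraceptives as a method of contraception must also use a barrier".
- **Section 4.1.1** also says of hormonal methods: "Established proper use of hormonal contraceptives that inhibit ovulation also have a failure rate of < 1% per year". It refers to Appendix 8 for the list of methods.
- **Appendix 8** introduces its list with "Examples of contraceptive methods with a failure rate of < 1% per year include the following". An asterisk marks the combined pill and the transdermal patch, and its footnote reads: "Women using estrogen containing hormonal contraceptives as a method of contraception must also use a barrier such as a male condom". The entry "Progestogen-only hormonal contraception associated with inhibition of ovulation" has no asterisk.
- **Section 4.4.2.2** mentions a barrier only for ethinylestradiol products: "hormonal contraceptives containing the CYP3A substrate ethinylestradiol (with the concomitant use of a barrier method) is permitted".

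**The concern.** Section 4.4.1.2 reads as a report of a rule that exists elsewhere in the protocol, and it uses that rule to dispose of a safety issue. No other section contains the rule in that breadth. The places a site would consult when deciding whether a woman's contraception is acceptable carry a narrower one and give no pointer to the mycophenolate section.

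What is at stake is participant safety. Section 1.3.1 reports fetal malformations in rats and rabbits, and for that reason makes highly effective contraception a condition of taking part. If a woman's pill is made less reliable by her background drug and nobody tells her to add a barrier, the offset on which Section 4.4.1.2 relies is absent in practice.

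**Working it through.** No power, alpha or event figure is involved, so the check is a comparison of texts followed by a count.

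**1. Scope of the barrier rule, by place**

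| Place | Barrier required with |
|---|---|
| Section 4.4.1.2 | any hormonal contraceptive |
| Synopsis, inclusion criteria | estrogen-containing methods |
| Section 4.1.1 | estrogen-containing methods |
| Appendix 8, footnote | estrogen-containing methods |

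The broad rule stands in 1 place and the narrow rule in 3. Section 4.4.2.2 mentions a barrier for ethinylestradiol products only, so it does not extend the rule to non-estrogen methods.

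**2. Which methods fall in the gap**

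- Hormonal entries in Appendix 8: combined oral pill, transdermal patch, vaginal device, progestogen-only contraception, implants, injections = 6.
- Non-oral entries, for which the documents state no mycophenolate interaction: patch, vaginal device, implants, injections = 4.
- Entries that are or can be oral: 6 − 4 = 2 (combined pill, progestogen-only).
- The estrogen rule already covers the combined pill: 2 − 1 = 1.

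The entry left is progestogen-only contraception, and only in pill form. The intrauterine device is not counted because Appendix 8 does not say whether it is hormonal. Counting it would change nothing, since it is not oral: 7 − 5 = 2.

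**3. One patient taken through the texts**

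Take a woman on mycophenolate who uses an ovulation-inhibiting progestogen-only pill.

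- Section 4.1.1 says that ovulation-inhibiting hormonal methods, properly used, meet the failure-rate limit, and makes no exception for mycophenolate.
- Appendix 8 lists her method without the barrier mark.
- She uses no estrogen, so the barrier sentence in the synopsis and Section 4.1.1 does not reach her.
- Section 4.4.1.2 says she must use a barrier.

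The first three give one answer and the fourth gives another.

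**4. Do other provisions supply the barrier?**

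- The clause in Section 4.1.1 on local requirements for other standard-of-care drugs lengthens the period of contraception after the last dose. It adds no barrier.
- The interaction review at pre-enrollment adjudication, as described in Appendix 19, concerns CYP3A and BCRP. Mycophenolate is not among that appendix's examples.
- Regular pregnancy testing detects a pregnancy but does not prevent one.
- Male patients are not affected: with a partner of childbearing potential they must be abstinent or use a condom plus a second method.

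**The case against.** The best answer is that the safeguard is already in the protocol, in the section that governs mycophenolate. All the texts can be satisfied together by following the strictest of them, and staff managing a patient on mycophenolate may well read that section. On this view only a repetition or cross-reference is missing. Much of this stands. A reader might infer that the protocol has no barrier rule for the progestogen-only pill; that would be wrong. What remains is that the eligibility text and its appendix state a different rule without a pointer, so exact compliance with them does not deliver the barrier.

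The failure-rate criterion is also a real safeguard. It is set in terms of performance, Appendix 8 gives examples rather than blanket approval, and an investigator aware of the interaction could conclude that a pill alone does not qualify. But Section 4.1.1 tells that investigator that ovulation-inhibiting methods do qualify. It would therefore be too strong to call the barrier the only protection, and too generous to say that the criterion closes the gap.

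The stated interaction is itself only a possibility. The documents do not say whether it applies to progestogen-only pills in particular. Consent pages are not available here, so whether they deal with the matter is unknown.

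Two stronger readings are tempting:

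- **Users of implants, injections, the patch or the vaginal device are exposed as well.** The interaction is stated for oral contraceptives only, so the documents do not support this.
- **Mycophenolate started as escape therapy opens a separate, unguarded route.** Read literally, the barrier sentence in Section 4.4.1.2 does not depend on when mycophenolate starts. Section 4.3.2.3.4 requires discussion with the Medical Monitor before a patient on escape therapy stays on study drug, and Section 4.6.2 ties new lupus treatment to Medical Monitor approval. Those sections do not mention contraception, so the rule should name later starts, but this adds little to the point.

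**Conclusion.** The inconsistency holds, and it is more than a matter of style: two rules of different breadth cover the same women, and the texts used for eligibility carry the weaker one. Its practical reach is a woman on mycophenolate who takes a progestogen-only pill, which is one of the six hormonal entries in Appendix 8 and only in pill form. The number of such women is not given and may be zero.

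The conclusion assumes that the interaction as worded, with oral contraceptives in general, includes progestogen-only pills. Section 4.4.1.2 names mycophenolate mofetil in the interaction sentence; treating mycophenolic acid alike follows from that section's handling of the two as interchangeable at equivalent doses.

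No endpoint, power statement or analysis is affected, and a reader should not infer any effect on the trial's efficacy conclusions. The change is worth making because the potential harm is serious and the correction is very cheap.

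**What to change.** Add one sentence to the synopsis, Section 4.1.1 and Appendix 8:

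> Women taking mycophenolate mofetil or mycophenolic acid, whether at entry or started later, who use any oral hormonal contraceptive, including a progestogen-only pill, must also use a barrier (see Section 4.4.1.2).

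Then align the wording of Section 4.4.1.2 with the final rule, so that all four places say the same thing. Whether the rule should also reach non-oral hormonal methods is for the sponsor's safety staff: the present wording of Section 4.4.1.2 would include them, but the documents state no interaction for them.

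The cost is a minor text edit and a small added burden for the women concerned. Nothing in the statistical analysis changes.

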#### **4.4.1.3 Azathioprine**

*It is strongly recommended that* prior to starting azathioprine, patients should have been evaluated for thiopurine methyltransferase variant alleles that have been associated with decreased activity in vitro and lead to the accumulation of the drug and/or its metabolites. A stable dose *used* for at least 8 weeks duration prior to screening of up to 2.5 mg/kg/day is allowed.

#### **4.4.1.4 Methotrexate**

Treatment must have been stable for at least the 8 weeks before screening. Patients taking methotrexate (oral or parenteral) must stay on the same dose delivered by the same route for the duration of their participation in this study. To prevent methotrexate-

associated adverse events, all patients on methotrexate are required to take folic acid (e.g., 1 mg/day) or equivalent at a stable dose of at least 5 mg/week or equivalent *as per local standard of care*.

#### **4.4.1.5 Non-Steroidal Anti-inflammatory Drugs**

As needed use of NSAIDs should be avoided within 24 hours before a visit where clinical efficacy assessments are scheduled to be performed and recorded.

Aspirin can be taken to reduce cardiovascular risk, but the dose is not to exceed 325 mg/day.

In order to prevent NSAID-related GI complications in high-risk patients, concomitant acid reducing agents (e.g., PPIs) should be used according to local guidelines (see Section [5.1.1.3](#)).

*Note that patients on anti-platelet agents may not be taking aspirin at the same time.*

#### **4.4.1.6 ACE Inhibitors and ARBs**

For patients who are on ACE inhibitors or ARBs at study entry, *it is strongly recommended that* doses of ACE inhibitors or ARBs be kept stable for at least 10 days prior to randomization and throughout the trial whenever possible. *It is strongly recommended that* ACE inhibitors or ARBs *not* be initiated during the OCS stability windows.

#### **4.4.1.7 Dietary Supplements**

For the purposes of this protocol, dietary supplements are defined as vitamins, minerals, purified food substances, and herbals with pharmaceutical properties. Vitamins, minerals, and purified food substances are allowed in amounts not known to be associated with adverse events (e.g., hypervitaminosis). Herbals with pharmaceutical properties are allowed only if there is acceptable evidence of no CYP3A inhibition or induction (refer to [Appendix 19](#)).

for a list of prohibited concomitant medications, including herbal products). Otherwise, herbals with pharmaceutical properties must be discontinued for at least 4 weeks prior to the first dose of study medication, unless there is sufficient data available regarding the duration of an herbal medication's PK and PD effects to allow a shorter washout to be specified (e.g., 5 half-lives). Please direct any questions to the Medical Monitor.

#### **4.4.1.8 Acid Reducing Agents**

Patients who use short-acting antacids (e.g., Maalox®, Pepto-Bismol®, Roloids® for symptomatic relief of heartburn) should take GDC-0853 or matching placebo 2 hours before or 2 hours after short-acting antacid administration because gastric acid improves GDC-0853 absorption. Patients may be treated with PPIs or H2RAs at up to the maximum recommended dose according to local labeling. The dose should remain stable for at least the 2 weeks before randomization and throughout the study. At visits

with scheduled PK assessments (see [Appendix 1](#) and [Appendix 2](#)), *the date and time of last administration of any PPIs, H2RA, and/or short-acting antacids taken* should be recorded *on the concomitant medication eCRF*.

